In the planning of the PAODEX Trial a small pilot study (10 patients) was launched for the clinicians to have some empirical data to support their clinical hypothesis (e.g., practical for power and sample size considerations). Two patients were exposed to perioperative DXMT administration (participants #9 and #10), whereas data was collected “as usual” from 8 patients (#1-#8; corresponding to placebo *per se*). Based on the sparse data available from the pilot study, basic descriptive statistics indicate that the overall mean is 47.47 mg morphine (over the 48 hours primary interest), with a standard deviation (SD) of 32.69 mg morphine; these descriptive statistics together with the overall median (57.9 mg morphine) suggests that data might not be normally distributed, however. Although questionable - because of the small sample sizes - the mean (SD) in the placebo and DXMT group corresponded to 56.8 (32.2) and 20.0 (14.1) mg morphine, respectively. We note that the poorly controlled – but potential clinical effect of adding DXMT – could correspond to an estimated treatment difference of promising 36.8 mg morphine *per se* (i.e., potential net benefit).

For a two-sample pooled t test of a normal mean difference with a two-sided significance level of 0.05, assuming a common standard deviation of 40 mg morphine, a total sample size of 87 patients assuming an allocation ratio of 2 to 1 (corresponding to group A&B vs group C) is required to obtain a power of at least 90% to detect an estimated treatment difference of 30 mg morphine. It was decided to aim for enrolment of 90 participants in total (randomised: 30:30:30; i.e., $n_A + n_B = 60$ vs $n_C = 30$).

Based on the same assumptions as above, even if we are only able to enrol and randomise 66 patients in total (allocation ratio of 2 to 1; i.e., approximately 44 vs 22 patients) we will obtain a reasonable statistical power of 80%.

According to our key secondary efficacy objectives we also want to compare the effect of double dose (Group A) with a single dose (Group B) of intravenous DXMT: For a two-sample pooled t test of a normal mean difference with a two-sided significance level of 0.05, assuming a common standard deviation of 40 mg morphine, a total sample size of 60 patients assuming a balanced design ($n_A = n_B = 30$) has a statistical power of 81.5% to detect an estimated treatment difference of 30 mg morphine (still assuming that the SD is around 40 mg).

Timing of final analysis

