The overall study design is based on three groups (A, B, and C); we apply linear modelling based on general linear models (GLMs) in the analysis of the primary and key secondary outcome measures (all continuous outcome measures): Analysis of covariance (ANCOVA) models will be performed, which produces several diagnostic measures, provides contrasts and estimates for customised hypothesis tests, and it provides tests for means adjusted for covariates (e.g., least squares [LS] means adjusted for baseline variables). The GLM procedure handles models relating a continuous dependent variable to one or several independent variables. The main statistical estimand from these analyses will be the difference between the least squares mean reported with 95% Confidence Intervals (95%CIs). Categorical outcomes related to dichotomous endpoints will be analysed with the use of logistic regression with the same fixed effects and covariates as the respective analysis of covariance; for ease of interpretation the resulting Odds Ratios (95%CI) will subsequently be converted into Risk Differences with 95%CIs.

The independent variables can be either classification variables, which divide the observations into discrete groups (e.g., A&B and C, respectively), or continuous variables (e.g., the level at baseline). As stated above, we will analyse continuous outcomes using ANCOVA models, with a fixed factor for group (either 2

levels for primary models [A&B pooled vs C] or 3 levels for the secondary analyses [A vs B vs C], respectively) and adjust for the value at baseline.

For the secondary objectives comparing all three groups, each continuous outcome variable (after performing the overall ANCOVA model), obtain the *P*-value and group contrast for the difference between the LS means: A vs. B (in analogy to a two-sample t test), independent of what the overall ANCOVA model indicates. Also, results following the ANCOVA model will be expressed as estimates of the group difference in the various pairwise comparisons in the changes from baseline, with 95% CIs to represent the precision of the estimates.

To assess the adequacy of the linear models describing the observed data, as well as to check the assumptions for the systematic and random parts of the models, we will investigate the model features via the predicted values and the residuals; that is, the residuals have to be normally distributed (around 0) and be independent of the predicted values.

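### The primary ANCOVA merges the two dexamethasone arms into one factor level, so any dose difference inflates its residual; a three-level model with a pre-specified contrast answers the same question slightly more precisely

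*SAP*

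**What the plan says.** Under Trial design, the SAP describes three parallel groups allocated 1:1:1. Under Statistical analyses and multiplicity considerations, the primary null hypothesis compares any dose of dexamethasone (A&B) with placebo (C). The ANCOVA group factor there has either two "levels for primary models [A&B pooled vs C] or 3 levels for the secondary analyses [A vs B vs C], respectively". The same section notes that the procedure can produce customised contrasts, but assigns none to the primary test.

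Under Sample size and power calculation, the primary comparison is planned as a pooled t test at the two-sided 5% level, with an SD of 40 mg in every group. The target is a 30 mg difference with power of 90% or more, for which the SAP states: "a total sample size of 87 patients assuming an allocation ratio of 2 to 1 (corresponding to group A&B vs group C) is required". Enrolment is then set at 90 (30 per arm). The same section plans double versus single dose separately, with the same SD, and finds that a comparison of 30 with 30 patients "has a statistical power of 81.5% to detect an estimated treatment difference of 30 mg morphine".

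**The concern.** The trial controls how many patients receive each dose. A difference between A and B is therefore a fixed feature of the design and not sampling error in the mean of the pooled group. A two-level model cannot represent it and counts it as noise. The estimate of A&B versus C is unbiased, but its reported standard error is too large whenever the doses differ.

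The SAP takes a dose difference seriously enough to power it at 30 mg, so the question is how much precision the primary analysis gives up if such a difference exists. There is also a small reporting consequence. Tables 2 and 4 both report placebo least squares means with standard errors in the ITT population. Filled from two models, the same placebo patients would be shown with two different standard errors.

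**Working it through.** **Inputs (SAP, Sample size and power calculation).** Two-sided alpha 0.05, common SD 40 mg, difference 30 mg, 2:1 allocation, 87 required and 90 planned; for A vs B, 30 mg with 30 per arm. The SAP gives no correlation with baseline, so no covariate gain is counted.

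**Step 1: the plan's own figures.** Noncentral t, with noncentrality 30 / (40 × √(1/n1 + 1/n2)) and n1 + n2 − 2 df:

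| Comparison | Stated power | Recomputed |
|---|---|---|
| 58 vs 29 (N = 87) | at least 90% | 90.3% |
| 60 vs 30 (N = 90) | – | 91.3% |
| 44 vs 22 (N = 66) | 80% | 80.8% |
| 30 vs 30 (A vs B) | 81.5% | 81.5% |

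All reproduce.

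**Step 2: two-level model when A and B differ by D.** With 30 patients in each arm, the true standard error of the pooled difference does not depend on D: 40 × √(1/60 + 1/30) = 8.94 mg. The residual sum of squares divided by 40² is noncentral chi-square on 88 df, with noncentrality (30 × 30 / 60) × D² / 40². At D = 30 this is 15 × 900 / 1600 = 8.44. The expected residual variance is 1600 × (1 + 8.44/88) = 1753, a residual SD of 41.9 mg. The interval is too wide by about 41.9/40 = 1.047, or 4.7%; the simulated mean width is 37.1 mg against 35.5 mg.

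**Step 3: power at an average effect of 30 mg.** Two-level power integrates over the residual distribution in Step 2. The contrast 0.5*A + 0.5*B − C uses noncentral t with 87 df. At N = 90:

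| A−B (mg) | Two-level | Three-level contrast | Gain (points) |
|---|---|---|---|
| 0 | 91.3% | 91.3% | 0.0 |
| 10 | 91.1% | 91.3% | 0.2 |
| 15 | 90.9% | 91.3% | 0.4 |
| 20 | 90.6% | 91.3% | 0.7 |
| 30 | 89.7% | 91.3% | 1.6 |

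At D = 30, the figures are 88.6% vs 90.3% for N = 87, and 78.1% vs 80.7% for N = 66. Simulation of 400,000 trials at N = 90 and D = 30 gave 89.8% vs 91.3%.

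**Step 4: type I error.** With a zero average effect and D = 30, the two-level test rejects in 4.0% of trials, against the nominal 5%.

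**Step 5: placebo standard error, D = 30.** Two-level: 41.9/√30 = 7.6 mg. Three-level: 40/√30 = 7.3 mg.

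**Step 6: unequal variances.** Simulated type I error with 30 per arm and a zero average effect. The first SD pair is the pilot's; the others are illustrative.

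| SD dexamethasone / placebo | A−B (mg) | Two-level | Three-level contrast |
|---|---|---|---|
| 14.1 / 32.2 | 0 | 12% | 12% |
| 14.1 / 32.2 | 30 | 7.4% | 12.1% |
| 25 / 40 | 30 | 6.8% | 9.0% |
| 30 / 40 | 30 | 5.7% | 7.4% |

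**The case against.** **Power.** A reader might infer that the stated 90% power fails, or that the two sample-size calculations contradict each other. The SAP does not support this. It presents two separate calculations and never says that both 30 mg differences hold together. In that combined case the shortfall at the planned 90 patients is 0.3 points, and it is gone at A-B differences of 20 mg or less. Entering an inflated SD in the t-test formula overstates the loss (residual SD 41.9 mg gives 88.7% at N = 90), because the true standard error does not grow with D.

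**Plausibility.** The combined case is extreme. Against the pilot placebo mean of 56.8 mg, an average effect of 30 mg with A-B of 30 mg means 11.8 mg in A and 41.8 mg in B. The arms are treated alike until the 24-hour dose, so B's expected use before it would be at most 11.8 mg and its use afterwards at least 30 mg. Smaller differences, with gains below one point, are more realistic. This stands.

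**Unequal losses.** A reader might also infer that the pooled target shifts with dropout. Planned multiple imputation of missing outcomes largely removes this in the ITT analysis; it remains mainly for the per-protocol set.

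**Unequal variances.** If the dexamethasone arms vary less than placebo, both tests can exceed 5%, and the contrast by more when the doses differ. This limits the word conservative to the equal-variance case. It does not favour the two-level model: with A = B and the pilot SDs, both reject at about 12%. The fault is the common-variance assumption, which the two-level model only partly masks when the doses differ. The pilot dexamethasone SD rests on two patients.

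**Fit to the hypothesis.** The two-level model matches the stated null hypothesis and the planning t test, and it introduces no bias. That is correct, but with equal arms the contrast tests the same hypothesis and estimates the same effect.

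**Conclusion.** The point holds as a small, nearly free improvement in efficiency. The primary model ignores a distinction that was randomised. Under a common SD, this makes the primary interval too wide and the test conservative to the extent that the doses differ. The largest case examined (SD 40 mg, average effect 30 mg, A-B 30 mg, equal arms) costs 1.6 points of power at N = 90 and about 5% in interval width; with no dose difference it costs nothing. That combined case is an assumption of this review, not a statement in the SAP. The sample size is correctly calculated, and pooling the doses for the primary question is not in dispute. Two standard errors for placebo in Tables 2 and 4 would be an untidy result of using two models, not an error: Table 4 is labelled optional and exploratory.

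**What to change.** In Statistical analyses and multiplicity considerations, replace the choice between a two-level and a three-level factor with one three-level model (A, B, C) per continuous outcome. Name the contrast 0.5*A + 0.5*B - C as the primary test and estimate, and take A vs B from the same model. Fill Tables 2 and 4 from that model.

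The cost is a line of SAP text, one ESTIMATE statement in SAS and one residual degree of freedom (87 instead of 88). If A and B are equal, the power loss at N = 90 is about 0.007 points. Because the pooled-variance test is valid only when arm variances are similar, the text should say so. When the dexamethasone arms are less variable and the doses differ, the contrast no longer has the inflated residual to mask the problem.

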The final analysis for the between-group comparison (placebo versus DXMT) for the primary endpoint is planned to be performed after each randomised patient has completed 8 weeks follow-up. The main trial publication will be prepared when these data have been received and cleaned (anticipated by April 2023).

In subsequent manuscripts, secondary long-term endpoints will be analysed when the 12 months (anticipated January 2024) have been reached for all randomised patients followed by preparation of manuscripts.

STATISTICAL PRINCIPLES

Analysis populations

The primary analyses will be based on the intention-to-treat (ITT) population. Thus, all data from individuals randomised regardless of dropout and participation rate will be included in the ITT analysis belonging to the initially allocated. In general, it is advantageous to demonstrate a lack of sensitivity of the principal trial results to alternatives of the set of participants analysed (i.e., other analysis populations).

For the main analysis, we will conduct analyses of the full analysis set (according to the ITT population, using appropriate statistical techniques to handle missingness), and two subsequent sensitivity analyses (A) a per protocol analysis, as well as (B) a non-responder imputation so that any differences between them can be explicitly discussed and interpreted. The per protocol population will be defined as participants who were (i) randomised, AND (ii) had the intended prescription (randomly allocated intervention), AND (iii) had a successfully measured primary endpoint.

Statistical analyses and multiplicity considerations

The primary null hypothesis is based on the comparison between participants randomised to any dose of DEXA (group A&B) vs C; $H_0: \mu_{A+B} = \mu_C$.

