The CONSORT flowchart will comprise number of patients screened, excluded (with reasons) eligible for inclusion in the trial, randomised, receiving their allocated treatment, withdrawals (with reasons), and lost to follow-up (with reasons), included in the ITT analysis, included in per protocol analysis, and included in as treated analysis. The CONSORT flowchart is depicted in **Figure 1**.

Withdrawal / follow-up

The level of consent withdrawal will be classified as the following two options: 1) consent to continue follow-up and data collection and 2) complete withdrawal with no further follow-up and data collection. Timing of withdrawal and loss to follow-up will be presented in the CONSORT flowchart with numbers and reasons for withdrawal and/or loss to follow-up. Furthermore, the number (with reasons) of loss to follow-up during the course of the trial will be summarised by treatment group.

Missing data and sensitivity analyses

Statistical methods to handle missing data: Loss to follow-up (and missing data for various reasons) is hard to avoid in randomised trials. We will apply the analysis framework suggested by White et al for “ITT analyses” that depends on making plausible assumptions about the missing data and including all participants in sensitivity analyses:

1. Attempt to follow up all randomised participants, even if they withdraw from allocated treatment
2. Perform a main analysis of all observed data that are valid under a plausible assumption about the missing data (i.e., ‘Missing At Random’ [MAR], applying multiple imputation to handle missing outcome data)
3. Perform sensitivity analyses to explore the effect of departures from the assumption made in the main analysis (i.e., using both the Per Protocol population as well as the simplistic non-responder imputation).
4. Account for all randomised participants, at least in the sensitivity analyses.

The evaluability assessment of each participant in the statistical analyses will be performed before the code is revealed. Excluded participants and missing, unused or false data will be described.

Protocol deviations will be reported (defined as a failure to adhere to the protocol such as the wrong intervention being administered, incorrect data being collected and documented, errors in applying inclusion/exclusion criteria or missed follow-up visits). These will be defined as major or minor.

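### The primary 95% CI relies on equal residual variances in a 60 versus 30 comparison, and the SAP has no protection if placebo patients vary more

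*SAP*

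**What the plan says.** The section Statistical analyses and multiplicity considerations sets the contrast: "The primary null hypothesis is based on the comparison between participants randomised to any dose of DEXA (group A&B) vs C". For the model it states: "we will analyse continuous outcomes using ANCOVA models, with a fixed factor for group". The group factor has two levels in the primary model, the baseline value is the covariate, and the result is the LS-mean difference with its 95% CI. The SAP does not mention a robust standard error or a variance per group.

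The same section says that predicted values and residuals will be examined and that "the residuals have to be normally distributed (around 0) and be independent of the predicted values". It names no action if that condition fails.

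Missing data and sensitivity analyses explores departures from the main assumptions "using both the Per Protocol population as well as the simplistic non-responder imputation". No other sensitivity analysis is planned.

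Sample size and power calculation uses a pooled two-sample t test, "assuming a common standard deviation of 40 mg morphine, a total sample size of 87 patients", and settles on 60 versus 30. It also reports the pilot: "the mean (SD) in the placebo and DXMT group corresponded to 56.8 (32.2) and 20.0 (14.1) mg morphine". Those figures come from 8 and 2 patients, and the SAP itself calls them questionable.

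**The concern.** The single residual variance is not spelled out. It is the default of the named model, and it matches the pooled t test and common SD behind the sample size. In a balanced comparison it would matter little. Here, pooling two arms against one makes the comparison 2:1, and the common variance is then dominated by the larger dexamethasone group, while the uncertainty of the difference comes mostly from the smaller placebo group. If placebo patients vary more, the standard error is too small; if they vary less, it is too large.

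Unequal spread is plausible. A morphine total cannot be negative, so a treatment that lowers the mean may also compress the SD.

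The per-protocol and non-responder analyses change which patients or imputed values enter, not the variance assumption. An analyst who finds unequal spread must either report an interval that fails the SAP's own check or choose a remedy after seeing the data.

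**Working it through.** **Inputs from the SAP.** Group sizes 60 and 30 (fallback 44 and 22); planning SD 40 mg; planned difference 30 mg; two-sided 5% level; pilot SDs 32.2 mg (placebo) and 14.1 mg (dexamethasone); pilot placebo mean 56.8 mg. All other SDs below are assumptions.

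**1. The plan's own figures.** Power of the pooled t test comes from the noncentral t distribution with noncentrality 30/(40·√(1/n₁+1/n₂)). At 58 versus 29 this is 30/9.10 = 3.30 on 85 df, giving 90.3%. At 44 versus 22 power is 80.8%, at 30 versus 30 it is 81.5%, and at 60 versus 30 it is 91.3%. The SAP's 87 patients, 80% and 81.5% all reproduce, so the sample size is not in question.

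**2. Model SE against true SE at the pilot SDs, 60 versus 30.**

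- Pooled variance: (29·32.2² + 59·14.1²)/88 = 475
- Model SE: √(475·(1/30 + 1/60)) = 4.87 mg
- True SE: √(32.2²/30 + 14.1²/60) = 6.15 mg
- Ratio: 4.87/6.15 = 0.79

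With the two SDs swapped, the SEs are 6.17 and 4.89 mg, ratio 1.26: the interval is then too wide.

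**3. How firm the pilot ratio is.** The variance ratio is (32.2/14.1)² = 5.2 on 7 and 1 df, two-sided p = 0.65, and the 95% CI for the SD ratio is 0.07 to 6.5. The pilot is compatible with equal or reversed SDs.

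**4. Coverage of the common-variance 95% CI** (100,000 simulated two-group trials per case, normal data, 60 versus 30 unless stated):

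| Placebo / dexamethasone SD (mg) | Coverage |
|---|---|
| 40 / 40 | 95.0% |
| 40 / 35 | 94.0% |
| 40 / 30 | 92.6% |
| 40 / 20 | 89.0% |
| 32.2 / 22.1 | 91.7% |
| 32.2 / 15.2 | 88.4% |
| 32.2 / 14.1 (pilot) | 87.8% |
| 14.1 / 32.2 (pilot reversed) | 98.6% |
| 32.2 / 14.1, 44 versus 22 | 87.9% |
| 32.2 / 14.1, 30 versus 30 | 94.9% |

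The rows with 22.1 and 15.2 mg do not use the two dexamethasone patients. They take the untreated mean of 56.8 mg and the planned 30 mg effect, so a treated mean of 26.8 mg. The variance then scales with the mean (32.2·√(26.8/56.8) = 22.1) or the SD does (32.2·26.8/56.8 = 15.2). The last row shows that the 2:1 pooling is what matters. Skewness is not: gamma data at the pilot SDs give 87.7%.

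A difference between the two doses adds to the pooled group's residual variance and offsets part of the error. At the pilot SDs with a dose difference of 10, 20 or 30 mg, coverage is 88.5%, 90.3% and 92.8%.

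**5. The planned model form.** ANCOVA with one covariate (correlation 0.3, an assumption; 20,000 trials per case), ordinary against HC3 standard errors: 95.0 vs 95.2% at 40/40; 92.5 vs 95.1% at 40/30; 89.1 vs 95.1% at 40/20; 87.7 vs 95.0% at 32.2/14.1. Group-specific variances give 94.5 to 96.1% in every case. Multiple imputation was not simulated.

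**6. Size in milligrams.** At the pilot SDs the mean CI width is 19.3 mg with a common variance and 24.8 mg with group-specific variances, so each limit moves (24.8 − 19.3)/2 ≈ 2.8 mg. At 40/30 the widths are 29.8 and 33.1 mg, about 1.7 mg per limit.

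**7. The null test.** If the drug changes neither mean nor spread, rejection is 5.0%. If means are equal but SDs are as in the pilot, the common-variance test rejects in about 12%.

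**The case against.** Common-variance ANCOVA is a conventional primary analysis and agrees with the SAP's sample-size basis. Nothing in the SAP is contradicted, and the residual check would probably reveal unequal spread, because in a two-group model the predicted values largely separate the groups. That is fair, but detecting a problem does not help if no response is fixed in advance.

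The most striking coverage figure depends on an SD from two patients. The SAP did not plan on it: it chose 40 mg for both groups, where coverage is 95%. This stands. No document supports a particular SD ratio, and even the direction of the error is unknown. The case therefore rests on the whole range of scenarios and on a remedy that works in both directions.

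The practical effect is small. With a 30 mg effect, the significance verdict differs between the common-variance and Welch analyses in 1.6% of trials at SDs 40/35, 2.0% at 40/30 and 0.2% at the pilot SDs. This also stands and limits the weight of the point.

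The planned analysis uses multiple imputation, which the simulations omit. If the imputation model itself assumes a common variance, changing only the final standard error may not fully restore coverage. This remains open and should be covered in the fix.

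**Conclusion.** The point holds in conditional form. The primary interval depends on equal residual variances in a 2:1 comparison, and the SAP neither protects nor tests that assumption. If placebo is the more variable arm, coverage falls to about 94% for a mild difference (40/35), 92.6% at 40/30 and about 88% at the pilot SDs. If it is the less variable arm, the interval is too wide.

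The main risk is to the stated precision of the primary estimate when the drug works and also reduces spread. There is no inflation of the type I error if the drug does nothing at all; inflation would need equal means with unequal spread, which is less plausible. The conclusion on efficacy would seldom change. All SD ratios are assumptions, and results under multiple imputation are untested. The change is worth making because it costs little, not because the planned analysis is invalid.

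**What to change.** Keep the LS-mean difference as the primary estimate. In Statistical analyses and multiplicity considerations, state that for the pooled dexamethasone versus placebo contrast the SE and 95% CI use group-specific residual variances with Satterthwaite degrees of freedom, or HC3 standard errors. Choose one and name it. Compute it in each imputed data set and combine by Rubin's rules. State also that the imputation model will not force a common variance on the two groups.

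Report the common-variance ANCOVA as a sensitivity analysis. State that the residual check is descriptive and does not change the primary method. The check then no longer needs a consequence for unequal spread, because the primary interval already allows for it, and a data-driven switch is avoided.

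The cost is one model option in SAS and a few sentences. The estimate and sample size are unchanged. If SDs are equal at 40 mg, power goes from 91.3% to about 91.0% with group-specific variances (a loss of 0.3 to 0.4 points), or falls by 0.6 points with HC3. If placebo is more variable, the reported interval is wider, as it should be: 33.1 instead of 29.8 mg on average at 40/30.
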